6.2.1. Preparation and Dispensing

See the IP manual or package insert for instructions on how to prepare the investigational product for administration. Investigational product should be prepared and dispensed by an appropriately qualified and experienced member of the study staff (eg, physician, nurse, physician's assistant, nurse practitioner, pharmacy assistant/technician, or pharmacist) as allowed by local, state, and institutional guidance.

6.3. Measures to Minimize Bias: Randomization and Blinding

6.3.1. Allocation to Investigational Product

All eligible participants will be randomized in a 1:1 ratio to receive either 20vPnC or 13vPnC (control vaccine).

Allocation of participants to vaccine groups will proceed through the use of an interactive response technology (IRT) system (interactive Web-based response [IWR]). The site personnel (study coordinator or specified designee) will be required to enter or select information including but not limited to the user's identification (ID) and password, the protocol number, and the participant number. The site personnel will then be provided with a vaccine assignment, randomization number, and dispensable unit (DU) or container numbers when investigational product is being supplied via the IRT system. The IRT system will provide a confirmation report containing the participant number, randomization number, and DU or container numbers assigned. The confirmation report must be stored in the site's files.

The study-specific IRT reference manual and IP manual will provide the contact information and further details on the use of the IRT system.

6.3.2. Blinding of Sponsor

Sponsor personnel involved in evaluating participant data in the primary study population will be blinded to vaccine assignment until the final analysis at the completion of participation of the primary study population, following the principles outlined in International Council for Harmonisation (ICH) E9 guideline on Statistical Principles for Clinical Trials.⁷³ The study team will remain blinded to the vaccine assignments of the Russian cohort until that cohort has completed the study. A data blinding plan will be created to describe the blinding requirements and unblinding events. Laboratory personnel

performing the immunologic assays will be blinded until all assays have been completed and assay results finalized.

6.3.3. Breaking the Blind

The study will be participant- and investigator-blinded.

At the initiation of the study, the investigator site will be instructed on the method for breaking the blind for an individual participant. The method will be an electronic process. Blinding codes should be broken only in exceptional circumstances when knowledge of the actual treatment code is absolutely essential for further management of the participant. Investigators are encouraged to discuss with a member of the study team if they believe that unblinding is necessary. When the blinding code is broken, the reason must be recorded in the source documentation and entered on the CRF.

6.4. Study Intervention Compliance

All doses of investigational product will be administered by the appropriately designated study staff at the investigator site.

6.5. Concomitant Therapy

6.5.1. Prohibited Concomitant Vaccines and Treatments

- Receipt of any investigational vaccines, drugs, or medical devices is prohibited during study participation.
- Receipt of nonstudy pneumococcal vaccine is prohibited during study participation.
- No additional doses of the study concomitant vaccines are allowed during the study except as prescribed by the protocol (eg, only 2 infant and 1 toddler dose of Infanrix hexa can be given, and should be given consistent with the protocol).
- Receipt of blood/plasma products, immunoglobulins, and/or immunosuppressive therapy (including a ≥ 14 -day course of systemic corticosteroids) is prohibited during study participation.

6.5.2. Permitted Concomitant Vaccines and Treatments

- Licensed inactivated influenza vaccine may be given at any time during the study per national recommendations.
- Rotavirus vaccine may be given at any time during the study, and according to local or national recommendations.
- Meningitis B vaccine may be given during the study as per national recommendations. It must be given at least 2 weeks before and/or 2 weeks after scheduled study vaccinations, and in accordance with local recommendations.

- Receipt of meningococcal conjugate vaccines is permitted after the blood draw at Visit 5.
- Receipt of other licensed nonstudy vaccines is permitted after the Visit 5 blood draw.
- Use of topical anesthetic is permitted during the study per local practice.
- The use of prophylactic antipyretic/pain medication, while permitted, is not recommended on the day of investigational product administration (before or after vaccination). If symptoms develop, the use of antipyretic/pain medication is allowed.
- Inhaled/nebulized, topical (skin, eyes, or ears), or localized injections of corticosteroids (eg, intra-articular or intrabursal administration) are permitted during participant participation in the study.
- Prescription and nonprescription medications, vitamins, minerals, and herbal remedies are permitted during the study.

6.5.3. Prior Vaccines and Treatments

- A birth dose of bacille Calmette-Guérin (BCG) vaccine may be given at least 28 days before vaccination with the first dose of investigational product.
- Receipt of hepatitis B vaccine at birth is permitted but must be at least 28 days before the first vaccination of investigational product.

6.5.4. Recording Prior and Concomitant Vaccines and Treatments

The name and date of administration for all vaccinations should be collected from the time of signing of the ICD to Visit 5 and will be recorded in the CRF. At Visit 1, information on prior vaccinations will also be recorded in the CRF. Vaccines required by the protocol, as well as those not stipulated, will be recorded throughout study participation. Information on vaccines given to the mother during pregnancy and any intrapartum antibiotic use will also be collected (at Visit 1 only), if available.

Medications taken to treat SAEs and NDCMCs from the signing of the ICD to the final visit (Visit 5) will be recorded on the CRF.

6.6. Dose Modification

Not applicable.

6.7. Intervention After the End of the Study

No intervention will be provided to study participants at the end of the study.

7. DISCONTINUATION OF STUDY INTERVENTION AND PARTICIPANT DISCONTINUATION/WITHDRAWAL

7.1. Discontinuation of Study Intervention

Participant eligibility must be confirmed prior to each vaccination in order to continue in the study.

If a participant no longer meets the eligibility criteria during the vaccination period of the study, further vaccinations should be discontinued, but the participant may remain in the study. If a participant is discontinued from vaccination and the participant's parent(s)/legal guardian(s) consents, safety follow-up will be conducted as per [Section 8.3](#). AEs, SAEs, and NDCMCs will be collected for 1 month after the last study vaccination.

See the [SoA](#) for data to be collected at the time of intervention discontinuation and follow-up and for any further evaluations that need to be completed.

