To describe the safety profile of 20vPnC	
In participants receiving at least 1 dose of investigational product and having safety data reported after any vaccination in each vaccine group:
 
 • The percentage of participants reporting prompted local reactions within 7 days after each vaccination • The percentage of participants reporting prompted systemic events within 7 days after each vaccination • The percentage of participants reporting AEs from Dose 1 to 1 month after Dose 2 and from Dose 3 to 1 month after Dose 3 • The percentage of participants reporting SAEs through 1 month after Dose 3 	
 • Prompted local reactions (redness, swelling, and pain at the injection site) • Prompted systemic events (fever, decreased appetite, drowsiness/increased sleep, and irritability) • AEs • SAEs • NDCMCs

	
 The percentage of participants reporting NDCMCs through 1 month after Dose 3 	
Primary Pneumococcal Immunogenicity Objectives	Estimands	Primary Pneumococcal Immunogenicity Endpoints
To demonstrate that the percentages of participants with predefined serotype-specific IgG concentrations for the 13 serotypes in the 20vPnC group are noninferior to those of the corresponding serotypes in the 13vPnC group at 1 month after Dose 2	
In evaluable participants at 1 month after Dose 2:
 
 For each of the 13 matched serotypes: difference in the percentages of participants with predefined IgG concentrations between the 20vPnC group and the 13vPnC group 	
 Pneumococcal IgG concentrations
To demonstrate that the percentages of participants with predefined serotype-specific IgG concentrations for the 7 additional serotypes in the 20vPnC group are noninferior to the lowest among the 13 serotypes in the 13vPnC group at 1 month after Dose 2	
In evaluable participants at 1 month after Dose 2:
 
 For each of the 7 additional serotypes in 20vPnC: difference in the percentages of participants with predefined IgG concentrations between the 20vPnC group and the lowest percentage of participants with predefined IgG concentrations among the 13 serotypes from the 13vPnC group 	
 Pneumococcal IgG concentrations

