8.3.1. Time Period and Frequency for Collecting AE and SAE Information

The time period for actively eliciting and collecting AEs and SAEs ("active collection period") for each participant begins from the time the participant's parent(s)/legal guardian(s) provides informed consent, which is obtained before the participant's participation in the study (ie, before undergoing any study-related procedure and/or receiving investigational product), through and including Visit 3, and from Visit 4 through Visit 5. SAEs and NDCMCs will be recorded and reported from the signing of the ICD through the final visit (Visit 5). At Visit 5, the participant's parent(s)/legal guardian(s) will be asked to report any AEs and SAEs, including hospitalizations and NDCMCs, that have occurred since Visit 4.

Follow-up by the investigator continues throughout and after the active collection period and until the event or its sequelae resolve or stabilize at a level acceptable to the investigator, and Pfizer concurs with that assessment.

Investigators are not obligated to actively seek AEs or SAEs after conclusion of the study participation. However, if the investigator learns of any SAE, including a death, at any time after a participant has completed or withdrawn early from the study, and he/she considers the event to be reasonably related to the study intervention or study participation, the investigator must promptly notify the sponsor.

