2.2. Study Design

This Phase 3, multicenter, randomized, double-blind study will be conducted at investigator sites in the European Union and Australia (primary study population), with an additional cohort from Russia (Russian cohort).

The primary study population will consist of 1200 infants >36 weeks of gestation and ≥ 42 to ≤ 112 days of age at the time of consent by a parent(s)/legal guardian(s). Participants will be randomized in a 1:1 ratio to receive either 20vPnC or 13vPnC (control vaccine) by site-based randomization. Participants will receive the same vaccine (either 20vPnC or 13vPnC) for all 3 doses at roughly 2, 4, and 11 to 12 months of age (Doses 1, 2, and 3, respectively). A specific vaccine containing DTaP, HBV, IPV, and Hib antigens will be administered concomitantly with all doses of 20vPnC or 13vPnC. Vaccines containing MMR and varicella antigens are also to be administered with Dose 3. These vaccines are intended to be given to all participants. However, in case of circumstances due to local practice/recommendations, some sites may not administer them to their participants at Dose 3, in which case MMR and varicella vaccines will be considered nonstudy vaccines.

Blood will be drawn from all participants for immunogenicity assessments 1 month after Dose 2, immediately prior to receipt of Dose 3, and 1 month after Dose 3. A subset of participants, based on consent to additional optional blood draws offered at certain sites, will have blood collected for immunogenicity assessments prior to Dose 1 and prior to Dose 2. Participants will be observed for 30 minutes after each vaccination and any reactions occurring during that time will be recorded as AEs. Prompted local reactions (redness, swelling, and pain at the 20vPnC or 13vPnC injection site) and systemic events (fever, decreased appetite, drowsiness/increased sleep, and irritability), and use of antipyretic/pain medications occurring within 7 days after each vaccination will be collected via a provided e-diary (or e-diary application). AEs, including nonserious AEs, will be collected from the signing of informed consent to 1 month after Dose 2 and from Dose 3 to 1 month after Dose 3. SAEs and NDCMCs will be collected for the entire duration of the study.

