Dose 3 evaluable immunogenicity	
Any participants who
 
 1. Are eligible and randomized, 2. Are within the protocol-defined age window (ie, 42-112 days of age, inclusive) on the day of Dose 1, 3. Receive all 3 vaccinations as randomized, with Dose 3 received within the protocol-defined window (ie, 335-386 days of age, inclusive), 4. Have at least 1 valid immunogenicity result within 27 to 56 days, inclusive, after Dose 3, and 5. Have no other major protocol deviations as determined by the clinician. 
The Dose 3 evaluable immunogenicity population will be the primary analysis population for pneumococcal immunogenicity results after Dose 3.
 
The statistical analysis of concomitant immunogenicity results 1 month after Dose 3 will be primarily based on the Dose 3 evaluable immunogenicity populations restricted to those who also receive the appropriate concomitant vaccines at the Dose 3 visit.
 
Participants will be grouped according to their randomized vaccine in the immunogenicity analysis.

Population	Description
Safety	
All participants who receive at least 1 dose of the investigational product and have safety data assessed after any dose. Participants will be grouped according to the vaccine as administered in the safety analysis.
 
Safety data after Dose 3 will be summarized for participants in the safety population who receive Dose 3 with safety follow-up after Dose 3.

For the Dose 2 and Dose 3 evaluable immunogenicity population definitions, the blood collection window has been expanded by 1 extra day before and 14 days after the protocol-specified blood collection window of 28 to 42 days defined in the protocol, for consistency with established rules in the 13vPnC development program. The major protocol deviations will be determined by clinical review or medical monitor. A major protocol deviation is a protocol deviation that, in the opinion of the sponsor's clinician, would materially affect assessment of immunogenicity, eg, participant receipt of a prohibited vaccine or medication that might affect immune response or a medication error with a suspected decrease in potency of the vaccine. The sponsor's clinician will identify those participants with major protocol deviations before any unblinded analysis.

Local reactions and systemic events based on the e-diary will be summarized from participants with any e-diary data reported in the safety population.

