6.1.1.4. Serious Adverse Events and Newly Diagnosed Chronic Medical Conditions

6.1.1.4.1. Main Analyses

- Estimands:
 - The percentage of participants reporting SAEs from Dose 1 to 1 month after Dose 3 ([Section 2.1](#)).
 - The percentage of participants reporting NDCMCs from Dose 1 to 1 month after Dose 3 ([Section 2.1](#)).
- Analysis set: Safety population ([Section 4](#)).
- Analysis time point: Dose 1 to 1 month after Dose 3.
- Analysis methodology: For percentages, the 2-sided Clopper-Pearson CIs will be calculated for each vaccine group ([Section 5.2.1](#)).
- Intercurrent events and missing data: No missing values will be imputed except for partial SAE/NDCMC start dates ([Section 5.3](#)).
- Reporting results: The numerator (n) and the denominator (N) used in the percentage calculation, the percentage (%), and the corresponding 2-sided Clopper-Pearson 95% CI for participants reporting any SAEs/NDCMCs, by each SOC, and each preferred term within SOCs will be presented by vaccine group. SAEs and NDCMCs will be presented separately.

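### The protocol gives two different end points for SAE and NDCMC collection in infants who stop vaccination but stay in the study, and the SAP has no rule for the shorter one

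*Protocol*

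**What the plan says.** **Infants who stop vaccination.** Protocol Section 7.1 covers the infant who no longer meets eligibility: "further vaccinations should be discontinued, but the participant may remain in the study". With parental consent, "safety follow-up will be conducted as per" Section 8.3. The next sentence reads: "AEs, SAEs, and NDCMCs will be collected for 1 month after the last study vaccination". Section 7.2 repeats the 1-month limit immediately after separating withdrawal from further product alone from withdrawal that also covers study procedures or follow-up.

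**The general collection rule.** Section 8.3.1 states: "SAEs and NDCMCs will be recorded and reported from the signing of the ICD through the final visit (Visit 5"). Section 8.2 agrees. SAP Section 2.2 says "SAEs and NDCMCs will be collected for the entire duration of the study", and SAP Section 3.1.1.5 also runs collection to the end of the study. None of these makes an exception for infants who stop vaccination. Footnote j of the Schedule of Activities gives the 1-month limit to participants withdrawn from the study.

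**The analysis.** The protocol estimand is "The percentage of participants reporting SAEs through 1 month after Dose 3". SAP Section 6.1.1.4.1 has "The percentage of participants reporting SAEs from Dose 1 to 1 month after Dose 3", with a matching line for NDCMCs. The denominator is the safety population: "All participants who receive at least 1 dose of the investigational product and have safety data assessed after any dose". SAP Section 4 limits summaries of data after Dose 3 to infants who received Dose 3, but that does not restrict a percentage that starts at Dose 1. For SAEs and NDCMCs only partial start dates are imputed. No rule covers follow-up that ends early.

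**The concern.** Two instructions in adjoining sentences of Section 7.1 lead to different end dates. A site with an infant who has stopped vaccination could reasonably follow the sentence written for that case, or the general rule it cites, and sites may choose differently.

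Under the 1-month reading, an infant can count as event-free for months that the collection rule does not cover. SAEs and NDCMCs are primary safety endpoints. Infants who newly fail the eligibility criteria of Section 5.2 may do so because of a seizure, a serious chronic disorder or immunodeficiency, so they need not have average risk. What is at stake is whether ascertainment matches the period named in the estimand. No efficacy or noninferiority conclusion depends on it.

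**Working it through.** **The plan's own figure.** Protocol Table 7 gives the chance of at least 1 event among 600 infants. At a true rate of 0.4%, 1 − (1 − 0.004)^600 = 91.0%, as stated. The other four rows also reproduce. The calculation treats all 600 as fully observed.

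**Observed share of the window.** The visit windows come from the Schedule of Activities: Dose 1 at 42 to 112 days of age, Dose 2 at 42 to 63 days later, Dose 3 at 335 to 386 days of age, Visit 5 at 28 to 42 days after that. I assume nominal doses at 60, 120 and 360 days of age, Visit 5 at 390 days, and 1 month as 30 days. The Dose 1 to Visit 5 window is then 390 − 60 = 330 days. Across the windows it runs from 335 + 28 − 112 = 251 to 386 + 42 − 42 = 386 days.

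| When vaccination stops | Nominal share observed, f | Range over visit windows |
|---|---|---|
| After Dose 1 | 30/330 = 9% | 28/386 = 7% to 42/251 = 17% |
| Soon after Dose 2 | (60 + 30)/330 = 27% | (42 + 28)/386 = 18% to (63 + 42)/251 = 42% |
| Found ineligible at Visit 4 | (360 − 60)/330 = 91% | 223/265 = 84% to 344/372 = 92% |

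In the last row, eligibility is checked before each vaccination, and Section 8.10.4 has staff ask at Visit 4 about SAEs and NDCMCs since the previous visit. The infant is therefore covered up to Visit 4: 335 − 112 = 223 of 223 + 42 = 265 days at one extreme, and 386 − 42 = 344 of 344 + 28 = 372 days at the other.

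**Effect on the percentage.** Let d be the share stopping and p the true risk over the window, with a constant hazard. Then

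reported risk = (1 − d)p + d[1 − (1 − p)^f].

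For small p the relative understatement is close to d(1 − f). The documents give no value for d, so I take 1% to 10%:

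- After Dose 1: d × 0.909 = 0.9% to 9.1%.
- Soon after Dose 2: d × 0.727 = 0.7% to 7.3%.
- At Visit 4: d × 0.091 = 0.1% to 0.9%.

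**In absolute terms.** With an assumed p = 5% and d = 5% (30 of 600 per group), the full formula gives a reported risk of 4.77%, 4.82% or 4.98% in the three cases.

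**Against Table 7.** At a true rate of 0.4%, the 91.0% becomes 90.8% to 88.8% if all stop after Dose 1, or 90.8% to 89.2% if all stop soon after Dose 2, for d from 1% to 10%.

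**The case against.** The strongest reply is that the protocol does not truncate collection. Section 7.1 sends these infants to Section 8.3. The procedures for Visits 3, 4 and 5 (Sections 8.10.3 to 8.10.5) have staff ask about SAEs and NDCMCs since the previous visit, with no exception for an infant who is no longer vaccinated. Parents are asked to report significant illness and hospitalization throughout the study (Section 8.10.6). SAEs that the investigator learns of later still go to the sponsor's safety group (Section 8.3.1.1).

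This stands in part. A reader might infer that collection definitely stops at 1 month, or that nobody would ask after that. The documents support neither inference. But the contradiction remains, because the 1-month sentence sits in the paragraph written for these infants and recurs in Section 7.2. The later-report route is also weaker. It depends on the investigator becoming aware, CRF recording is specified for the active collection period (Section 8.3.1.2), and Section 8.3.1.1 covers SAEs but not NDCMCs.

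A second reply is that an infant who stops because of a new condition may already be counted. The percentage is of infants with at least one event, so a stopping condition that is itself an SAE or NDCMC puts the infant in that numerator, and later events of that type add nothing. This is fair and would shrink the effect. Higher subsequent risk in infants not yet counted would enlarge it. The documents do not say how often infants stop or why.

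**Conclusion.** The contradiction is real and affects a primary safety endpoint. Under the 1-month reading, ascertainment falls short of the stated estimand and the SAE and NDCMC percentages are somewhat understated, by about 0.1% to 9% in relative terms. That range rests on an assumed 1% to 10% stopping, the nominal schedule and a constant hazard. If Section 8.3 governs, this loss does not arise.

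The practical effect is probably small, and two stronger readings should be set aside:

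- **Biased group comparison.** A reader might infer this, but the objective is descriptive and SAP Section 6.1.1.4.1 plans only per-group percentages with Clopper-Pearson intervals for these endpoints. If a reader subtracts the groups anyway, 5% versus 2% stopping soon after Dose 2 (assumed, with a 5% true risk) shifts the difference by about 0.11 percentage points.
- **A ceiling from the 17% nonevaluable rate in Section 9.2.1.** That rate concerns immunogenicity evaluability, which Section 9.3 makes depend also on blood-draw and Dose 3 windows, valid results and major deviations. It does not bound the share of infants who stop vaccination but stay.

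Withdrawn infants raise the same denominator question, but for them the 1-month limit is not in conflict with footnote j.

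**What to change.** Reconcile Protocol Sections 7.1 and 7.2 with Section 8.3.1, footnote j of the Schedule of Activities, and the SAP. For infants who stop vaccination but remain in the study, state that SAEs and NDCMCs are collected through the planned Visit 5 date. A telephone contact is enough, and inclusion criterion 4 already requires that parents can be reached by telephone. Keep the 1-month limit for infants withdrawn from the study.

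If the 1-month limit is kept for all, add to SAP Section 6.1.1.4.1 how truncated follow-up enters the SAE and NDCMC percentages.

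The cost is a wording change and a few extra contacts for what is likely to be a small number of infants still in the study. No vaccination rule changes.
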